16.43 Correlative Analyses

Immunohistochemistry will be used to quantify levels of CD4, CD8, PD-1/CD279, and PD-L1 expression before and after treatment with pembrolizumab and will be used for change in baseline calculations at baseline and end of cycle 2. Qualitative measures of the strength of PD-1 and PD-L1 expression will use published standardized grading scales for categorical classification purposes.

16.5 Primary Endpoint Completion Date for [REDACTED] Reporting

For purpose of [REDACTED] reporting, the Primary Endpoint Completion Date (PECD) for this study is the time the last patient registered has been followed for at least 7 months.

16.6 Data Safety and Monitoring

- 16.61 The study statistician will review the study weekly to monitor accrual, endpoints and adverse events. Additionally, the Mayo Clinic Cancer Center (MCCC) Data Safety Monitoring Board (DSMB) is responsible for reviewing accrual and safety data for this trial at least twice a year, based on reports provided by the MCCC Statistical Office.
- 16.62 This study will be monitored by the Clinical Data Update System (CDUS) version 2.0. A full report containing cumulative CDUS data will be submitted quarterly to CTEP by electronic means. Reporting time points are: January 31, April 30, July 31, and October 31.
- 16.63 Adverse Event Stopping Rules: The stopping rules specified below are based on the knowledge available at study development. We note that the Adverse Event Stopping Rule may be adjusted in the event of either (1) the study re-opening to accrual or (2) at any time during the conduct of the trial and in consideration of newly acquired information regarding the adverse event profile of the treatment(s) under investigation. The study team may choose to suspend accrual

because of unexpected adverse event profiles that have not crossed the specified rule below.

Accrual will be temporarily suspended to this study if at any time we observe events considered at least possibly related to study treatment (i.e. an adverse event with attribute specified as “possible,” “probable,” or “definite”) that satisfy one of the following:

- if 2 or more patients in the first 10 treated patients (20%) experience a grade 4 or higher non-hematologic adverse event at least possibly related to treatment.
- if after the first 10 patients have been treated, 20% of all patients experience a grade 4 or higher non-hematologic adverse event at least possibly related to treatment.

We note that we will review grade 4 and 5 adverse events deemed “unrelated” or “unlikely to be related”, to verify their attribution and to monitor the emergence of a previously unrecognized treatment-related adverse event.

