8.1 Dose Modifications Based on Adverse Events

CTCAE System/Organ/Class (SOC)	ADVERSE EVENT	AGENT	ACTION**
Cardiac disorders	Myocarditis	pembrolizumab	Hold if grade 1 or 2. Administer corticosteroids as clinically indicated. Discontinue if Grade 3 or 4. Pembrolizumab should be permanently discontinued if AE does not resolve within 12 weeks of last dose or corticosteroids cannot be reduced to ≤ 10 mg prednisone or equivalent per day within 12 weeks and continue to survival follow-up.
Endocrine disorders	Hyperthyroidism	pembrolizumab	Continue if grade 2. Treat with non-selective beta-blockers (e.g. propranolol) or thionamides as appropriate. ¹ Hold or discontinue if grade 3 or 4. If discontinue, continue to survival follow-up. Pembrolizumab should be permanently discontinued if AE does not resolve within 12 weeks of last dose and continue to survival follow-up.
	Hypophysitis	pembrolizumab	Hold if grade 2. Administer corticosteroids and initiate hormonal replacements as clinically indicated. ¹ Hold or discontinue if grade 3 or 4. Pembrolizumab should be permanently discontinued if AE does not resolve within 12 weeks of last dose or corticosteroids cannot be reduced to ≤ 10 mg prednisone or equivalent per day within 12 weeks and continue to survival follow-up.
	Hypothyroidism	pembrolizumab	Continue if grade 2-4. Initiate thyroid replacement hormones (e.g. levothyroxine or liothyroinine) per standard of care. Pembrolizumab should be permanently discontinued if AE does not resolve within 12 weeks of last dose and continue to survival follow-up.

CTCAE System/Organ/Class (SOC)	ADVERSE EVENT	AGENT	ACTION**
Gastrointestinal disorders	Diarrhea or Colitis	pembrolizumab	Hold if grade 2-3. Discontinue if Grade 4 or if AE does not resolve within 12 weeks of last dose or inability to reduce corticosteroid to 10 mg or less prednisone or equivalent per day within 12 weeks and continue to survival follow-up.
Immune System disorders	All other immune-related AEs	pembrolizumab	Hold if intolerable/persistent grade 2. Administer corticosteroids as clinically indicated. Hold if grade 3 AE, unless the event is Gullian-Barre Syndrome and/or Encephalitis, then, pembrolizumab should be discontinued. If AE does not resolve within 12 weeks of last dose or corticosteroids cannot be reduced to \leq 10 mg prednisone or equivalent per day within 12 weeks and continue to survival follow-up. Pembrolizumab should be discontinued if grade 4 AE or recurrent grade 3.

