Investigations	AST / ALT elevation or Increased Bilirubin	pembrolizumab	Hold if grade 2. Administer corticosteroids (initial dose of 1-2mg/kg prednisone or equivalent) followed by taper. Discontinue if Grade 3 or 4 or if AE does not resolve within 12 weeks of last dose or inability to reduce corticosteroid to 10 mg or less prednisone or equivalent per day within 12 weeks and continue to survival follow-up.
Metabolism and nutrition disorders	Type 1 diabetes mellitus (T1DM) or Hyperglycemia	pembrolizumab	Hold if Newly onset T1DM or Grade 3 or 4 hyperglycemia associated with evidence of β -cell failure. Initiate insulin replacement therapy for subjects with T1DM. Administer anti-hyperglycemic in subjects with hyperglycemia. Discontinue if AE does not resolve within 12 weeks of last dose and continue to survival follow-up.

CTCAE System/Organ/Class (SOC)	ADVERSE EVENT	AGENT	ACTION**
Renal and urinary disorders	Nephritis	pembrolizumab	Hold if grade 2. Administer corticosteroids (prednisone 1-2mg/kg or equivalent) followed by taper. Discontinue if grade 3 or 4 or if AE does not resolve within 12 weeks of last dose or inability to reduce corticosteroid to 10 mg or less prednisone or equivalent per day within 12 weeks and continue to survival follow-up.
Respiratory, thoracic and mediastinal disorders	Pneumonitis	pembrolizumab	Hold if grade 2. Administer corticosteroids (initial dose of 1-2mg/kg prednisone or equivalent) followed by taper. Discontinue if recurrent grade 2, if grade 3 or 4, or if AE does not resolve within 12 weeks of last dose or inability to reduce corticosteroid to 10 mg or less prednisone or equivalent per day within 12 weeks and continue to survival follow-up.
Skin and subcutaneous tissue disorders	Stevens-Johnson syndrome/ toxic epidermal necrolysis	pembrolizumab	Hold if grade 3. Discontinue if grade 4. Discontinue if AE does not resolve within 12 weeks of last dose and continue to survival follow-up.

** Use the following to describe actions in the Action column:

- **Omit** = The current dose(s) for the specified drug(s) during a cycle is skipped. The patient does not make up the omitted dose(s) at a later time.
- **Hold/Delay** = The current dose(s) of all drugs during a cycle is delayed. The patient does make up the delayed dose(s) when the patient meets the protocol criteria to restart drugs.
- **Discontinue** = The specified drug(s) are totally stopped.

NOTES:

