10.31 EXPECTED Serious Adverse Events: Protocol Specific Exceptions to Expedited Reporting

For this protocol only, the following Adverse Events/Grades are expected to occur within this population and do not require Expedited Reporting. These events must still be reported via Routine Reporting (see Section 10.6).*

*Report any clinically important increase in the rate of a serious suspected adverse reaction (at your study site) over that which is listed in the protocol or investigator brochure as an expedited event.

*Report an expected event that is greater in severity or specificity than expected as an expedited event.

*Specific protocol exceptions to expedited reporting should be reported expeditiously by investigators **ONLY** if they exceed the expected grade of the event.

CTCAE System Organ Class (SOC)	Adverse event/ Symptoms	CTCAE Grade at which the event will not be reported via expedited mechanisms ¹
Blood and lymphatic system disorders	Anemia	≤Grade 4
Gastrointestinal disorders	Vomiting	≤Grade 3
	Nausea	≤Grade 3
	Diarrhea	≤Grade 3
General disorders and administrations site conditions	Fatigue	≤Grade 3
	Malaise	≤Grade 3
Investigations	Neutrophil count decreased	≤Grade 4
	White blood cell count decreased	≤Grade 4
	Lymphocyte count decreased	≤Grade 4
	Platelet count decreased	≤Grade 4

CTCAE System Organ Class (SOC)	Adverse event/ Symptoms	CTCAE Grade at which the event will not be reported via expedited mechanisms ¹
Skin and subcutaneous tissue disorders	Rash (acneiform or maculopapular)	≤Grade 4

¹ These exceptions only apply if the adverse event does not result in hospitalization. If the adverse event results in hospitalization, then the standard expedited adverse events reporting requirements must be followed.

The following hospitalizations are not considered to be SAEs because there is no “adverse event” (*i.e.*, there is no untoward medical occurrence) associated with the hospitalization:

- Hospitalizations for respite care
- Planned hospitalizations required by the protocol
- Hospitalization planned before informed consent (where the condition requiring the hospitalization has not changed post study drug administration)
- Hospitalization for elective procedures unrelated to the current disease and/or treatment on this trial
- Hospitalization for administration of study drug or insertion of access for administration of study drug

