Nervous system: altered mental status, confusion, dizziness, insomnia
Neuromuscular & skeletal: arthritis, myositis, neck pain
Ophthalmic: uveitis
Renal: acute kidney injury
Respiratory: nasopharyngitis, oropharyngeal pain, pleural effusion, respiratory

failure

Miscellaneous: fistula, infusion related reaction

Uncommon known potential adverse events , $\geq 0.1\%$ to $<1\%$:

Cardiovascular: Vasculitis

Endocrine & metabolic: adrenocortical insufficiency, diabetic ketoacidosis, hypoparathyroidism, hypophysitis, type 1 diabetes mellitus

Gastrointestinal: duodenitis, gastritis, increased serum amylase, increased serum lipase, pancreatitis

Hematologic & oncologic: aplastic anemia, hemolytic anemia, immune thrombocytopenia, immunological signs and symptoms (hemophagocytic lymphohistiocytosis), lymphadenitis (histiocytic necrotizing lymphadenitis [Kikuchi lymphadenitis]), sarcoidosis

Hypersensitivity: anaphylaxis

Immunologic: organ transplant rejection (solid)

Infection: Systemic inflammatory response syndrome

Nervous system: demyelinating disease, encephalitis, exacerbation of myasthenia gravis, Guillain-Barre syndrome, meningitis, myasthenia (myasthenic syndrome), myasthenia gravis, neuropathy (autoimmune), paresis (nerve)

Neuromuscular & skeletal: myelitis, polymyalgia rheumatica, polymyositis, rhabdomyolysis

Ophthalmic: iritis

Renal: nephritis

The risk profile for pembrolizumab also includes two important potential risks: a) myasthenic syndrome, and b) an increased risk of severe complications (such as early severe graft versus host disease and veno-occlusive disease) of allogeneic transplant in patients with hematologic malignancies who have previously been treated with PD-1 inhibitors.

Since the last IB, Edition 21, a new identified risk of hypoparathyroidism has been added to the warnings and precautions section of the CCDS based on routine pharmacovigilance.

Per IB, Edition 23 a new risk of optic neuritis has been added to the Postmarketing Experience Adverse Reactions section of the CCDS based on routine pharmacovigilance.

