15.199a Patients should avoid receiving live vaccines within 30 days of study drug administration or per other study guidelines.

15.199b Patients who have undergone an allogenic bone marrow transplant, have an increased risk of severe complications including early GVHD, and venoocclusive disease, if they have previously been treated with pembrolizumab

15.199c Myocarditis has been reported and associated with pembrolizumab. Instruct patients to report chest pain, SOB, or dyspnea to study team immediately and/or seek emergency medical attention.

15.199d Autoimmune hematologic disorders including ITP and hemolytic anemia have been reported. Monitor blood counts closely and report any abnormalities to the study team.

15.199e Rare neurologic disorders including Guillain-Barre syndrome and myasthenia gravis have been reported. Instruct patients to report any neurologic symptoms including weakness, parasthesias or numbness, tingling to the study team immediately.

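### The only numeric toxicity trigger (16.63) leaves out related deaths and grade 4 immune events classified as hematologic, and the grade 3 immune events for which 8.1 calls for discontinuation

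*Combined protocol and SAP*

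**What the plan says.** **The trigger.** Under 16.63, accrual is temporarily suspended "if 2 or more patients in the first 10 treated patients (20%) experience a grade 4 or higher non-hematologic adverse event at least possibly related", meaning related to the drug. A second limb applies "if after the first 10 patients have been treated, 20% of all patients experience a grade 4 or higher non-hematologic adverse event", again if at least possibly related. Suspension of accrual is the only stated consequence.

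**Treatment-ending events in 8.1.** For myocarditis the action is "Discontinue if Grade 3 or 4". For pneumonitis it is "Discontinue if recurrent grade 2, if grade 3 or 4, or if AE does not resolve within 12 weeks of last dose", or if steroids cannot be reduced. AST/ALT or bilirubin elevation and nephritis also lead to discontinuation at grade 3, as do Guillain-Barre syndrome and encephalitis. Other immune-related events do so at grade 4 or recurrent grade 3. Section 8.0 makes the table strict for two cycles and guidance after that.

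**Immune blood toxicity.** Section 15.17 lists, at 0.1% to under 1%, "aplastic anemia, hemolytic anemia, immune thrombocytopenia, immunological signs and symptoms (hemophagocytic lymphohistiocytosis" among other entries. Section 15.199d adds: "Autoimmune hematologic disorders including ITP and hemolytic anemia have been reported".

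**Other oversight.** Section 16.6 has the statistician review the study weekly and the DSMB at least twice a year. It lets the team suspend accrual for unexpected event profiles and lets the rule be adjusted at any time. Section 16.34 brings adverse events into any decision to terminate. Sections 10.52 and 10.84 send deaths and serious adverse events to the sponsor within 24 hours, within their stated windows.

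**Sample size.** Under Amendment 4, accrual stops at 10 patients (16.1, 16.31).

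**The concern.** A toxicity trigger should count the harms that would make the team pause. This one filters on two conditions, grade 4 or higher and non-hematologic, and both remove drug-related harms that the protocol itself names. Adding grade 5 to the count does not bring a hematologic death back, because the organ-class filter applies at every grade.

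Two patients could die of related events classified as hematologic, or several could stop for grade 3 immune myocarditis, pneumonitis, hepatitis or nephritis, and the count would stay at zero. A report that the toxicity limit was not crossed would then be true but would say little. Safety is a secondary goal (2.21), and the drug is given here as initial systemic therapy.

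**Working it through.** **1. Inputs.** The limit is 2 of the first 10 treated patients (16.63). The cap is 10 patients (16.31). Listed frequencies of the four immune blood conditions are 0.1% to under 1% each, any grade (15.17). The documents give no rates by grade for this population, so every rate below is an assumption.

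**2. The plan's own figures.** 2/10 = 0.20, as stated. The plan gives no operating characteristics for the toxicity rule. With independent patients and true rate p, the chance of reaching the limit is

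P(X ≥ 2) = 1 − (1 − p)^10 − 10p(1 − p)^9.

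The efficacy interim look also needs 2 of 10, so the 16.33 table checks the formula. At p = 0.15, 0.20, 0.25, 0.30 and 0.35 it gives 0.456, 0.624, 0.756, 0.851 and 0.914, which match the first row of that table.

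**3. The rule as written.** Here p is the rate of related grade 4 or higher non-hematologic events.

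| p | P(limit reached) |
|---|---|
| 2% | 0.016 |
| 5% | 0.086 |
| 10% | 0.264 |
| 20% | 0.624 |

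**4. What enters the count.**

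| Event, at least possibly related | Named in | Counts under 16.63? |
|---|---|---|
| Grade 4–5 non-hematologic | 8.1, 15.17 | Yes |
| Death classified as hematologic | 15.17 names the conditions | No |
| Grade 4 immune event classified as hematologic | 15.17, 15.199d | No |
| Grade 3 myocarditis, hepatic elevation, nephritis, pneumonitis, Guillain-Barre syndrome, encephalitis | 8.1 (discontinue) | No |
| Recurrent grade 2 pneumonitis; recurrent grade 3 other immune event | 8.1 (discontinue) | No |

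**5. Size of the hematologic gap.**

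- At 1%: 1 − 0.9044 − 0.0914 = 0.004.
- At 4%, the sum of four conditions at a 1% ceiling each: 1 − 0.6648 − 0.2770 = 0.058.

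The listed frequencies cover all grades, so if they carry over to this population, grade 4 or higher events are rarer still.

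**6. Effect of pooling under one limit.** One hematologic and one non-hematologic event would together reach 2. Assume a 5% non-hematologic rate and no patient with both.

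- Adding 1 point (p = 6%): 1 − 0.5386 − 0.3438 = 0.118, against 0.086.
- Adding the 4-point ceiling (p = 9%): 1 − 0.3894 − 0.3851 = 0.225.

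**7. Effect of the cap.** With 10 patients in total there is no eleventh patient, so the second limb never operates. Once the tenth patient is enrolled, suspending accrual changes nothing, while treatment may run to 24 months (7.1).

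**The case against.** The strongest reply is that 8.1 governs the individual patient and 16.63 governs accrual, so different thresholds are not a contradiction. That stands. For the grade 3 events the documents support a request to reconcile the two sections, not a finding that either is wrong. A trigger on every discontinuation criterion in 8.1 would also catch hypothyroidism unresolved at 12 weeks; hypothyroidism is listed at 10% or more in 15.17, and the same row of 8.1 says to continue treatment at grades 2 to 4.

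Three stronger readings are tempting, and the documents do not support them.

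- **Nothing else watches toxicity.** The oversight listed above is real, Section 10.0 adds safety reports to the FDA, and 16.42 tabulates the maximum grade of each event type. What is missing is a threshold. The discretionary suspension clause refers to unexpected profiles, and 10.2 treats an event listed in Section 15.0 as expected unless its specificity or severity exceeds the listing.
- **Grade 4 immune cytopenias also escape expedited reporting through 10.31.** That table exempts anemia and count terms such as "Platelet count decreased", and only without hospitalization. It does not list the diagnosed immune conditions. Greater severity or specificity than expected restores expedited reporting, and 10.84 still applies to serious events.
- **A wider rule would fire far more often.** Any such contrast depends on grade-specific rates that the documents do not give.

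It is also fair that non-hematologic is undefined. Section 8.1 has no hematologic row and puts other immune-related events under immune system disorders. An immune cytopenia, or a hemorrhage or sepsis following one, might be coded so that it counts. The exclusion is certain only for events classified as hematologic, and that uncertainty is itself a reason to write the rule out.

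**Conclusion.** The point holds for the pre-specified numeric trigger. As written, related deaths and grade 4 immune-mediated events classified as hematologic do not count, and neither do the grade 3 immune events for which 8.1 calls for discontinuation. No other provision sets a limit that would make up for this.

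In frequency the hematologic part is small. Two or more such events in 10 patients have probability about 0.004 at a 1% rate and about 0.06 at 4%, assuming independent patients and that the 15.17 frequencies carry over to this population. The case for the change rests on the seriousness of the excluded events and its low cost. No figure is put on the grade 3 part, because the documents give no rates by grade.

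Amendment 4 narrows the consequence without removing it: the second limb has no role, and suspending accrual protects nobody after the tenth enrolment, but patients remain on treatment.

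**What to change.** 1. In 16.63, keep the limit of 2 of the first 10 treated patients. State that any at-least-possibly-related death counts, and that at-least-possibly-related grade 4 or higher immune-mediated hematologic events count, regardless of organ class. Isolated laboratory count decreases may stay excluded.
2. State that crossing the limit prompts review by the existing DSMB for patients still on treatment, as well as suspension of accrual. Mark the second limb as not applicable under Amendment 4.
3. The sponsor should reconcile 16.63 with the grade 3 discontinuation criteria in 8.1 and say whether those events prompt DSMB review. No clinical threshold is proposed here, and no patient's treatment rule changes.

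The cost is a wording amendment. Section 10.62 already collects grade 3 and 4 events regardless of attribution, deaths within 30 days, and later deaths at least possibly related, and the DSMB is in place. The downside of items 1 and 2 is an occasional extra review; under the assumptions in the check, the chance of reaching the limit rises from 0.086 to 0.118, or to 0.225 at the 4-point ceiling.

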16.63 Accrual Stopping Rule

The study design assumes that 2 patients will accrue per month, leading to a 26-month total accrual. At 6 months, if the total accrual is below 50% of the expected (fewer than 6 patients) then the significance and power will be much better than designed for and a sample size reduction may be called for. Consequently, we will update the design and may adjust sample size and/or duration of follow-up. At 6 months, if the total accrual is above 200% (more than 24 patients) then we may have lost significance and/or power and an increase in sample size or a lengthening of total observation time may be necessary. Consequently, we may pause accrual or update the design and may adjust the sample size to achieve the desired significance and power.

16.7 Inclusion of Women and Minorities

16.71 This study will be available to all eligible patients, regardless of race, gender, or ethnic origin.

16.72 There is no information currently available regarding differential effects of this regimen in subsets defined by race, or ethnicity, and there is no reason to expect such differences to exist. Therefore, although the planned analysis will, as always, look for differences in treatment effect based on race, the sample size is not increased in order to provide additional power for subset analyses.

16.73 The geographical region served by MCCC has a population which includes approximately 3% minorities. Based on prior MCCC studies involving similar disease sites, we expect about 3-5% of patients will be classified as minorities by race and about 30% of patients will be women. Expected sizes of racial by gender subsets are shown in the following table:

Accrual Estimates by Gender/Ethnicity/Race

Ethnic Category	Sex/Gender			
	Females	Males	Unknown	Total
Hispanic or Latino	5	4	0	9
Not Hispanic or Latino	11	11	0	22

Ethnic Category	Sex/Gender			
	Females	Males	Unknown	Total
Ethnic Category: Total of all subjects	16	15	0	31
Racial Category				
American Indian or Alaskan Native	0	0	0	0
Asian	0	0	0	0
Black or African American	4	5	0	9
Native Hawaiian or other Pacific Islander	0	0	0	0
White	12	10	0	22
Racial Category: Total of all subjects	16	15	0	31

Ethnic Categories: **Hispanic or Latino** – a person of Cuban, Mexican, Puerto Rico, South or Central American, or other Spanish culture or origin, regardless of race. The term “Spanish origin” can also be used in addition to “Hispanic or Latino.”

Not Hispanic or Latino

Racial Categories: **American Indian or Alaskan Native** – a person having origins in any of the original peoples of North, Central, or South America, and who maintains tribal affiliations or community attachment.

Asian – a person having origins in any of the original peoples of the Far East, Southeast Asia, or the Indian subcontinent including, for example, Cambodia, China, India, Japan, Korea, Malaysia, Pakistan, the Philippine Islands, Thailand, and Vietnam. (Note: Individuals from the Philippine Islands have been recorded as Pacific Islanders in previous data collection strategies.)

Black or African American – a person having origins in any of the black racial groups of Africa. Terms such as “Haitian” or “Negro” can be used in addition to “Black or African American.”

Native Hawaiian or other Pacific Islander – a person having origins in any of the original peoples of Hawaii, Guam, Samoa, or other Pacific Islands.

White – a person having origins in any of the original peoples of Europe, the Middle East, or North Africa.

